14. FINANCING AND INSURANCE

The sponsor will acquire an insurance policy to cover possible damage to the subject resulting from their participation in the study, in accordance with applicable local legislation; such coverage will be renewed periodically for the full duration of the study.

15. PUBLICATION POLICY

Institution and the investigator agree that the first publication shall be made in conjunction with the presentation of a joint, multi-center publication of the study results from all appropriate sites. If such a multi-center publication is not submitted within twelve (12) months after conclusion of the study at all sites or after Grifols confirms there will be no joint, multi-center publication, then institution and/or investigator shall have the right, at their discretion, to publish, either in writing or orally, the results of the study performed under the protocol, subject to the conditions outlined below:

1. The results of the study will be reported in the publicly accessible registry(ies).
2. Institution and/or investigator shall furnish Grifols with a copy of any proposed publication at least thirty (30) days in advance of the date of submission for publication.
3. Within said thirty (30) day period, Grifols shall:
 - Review such proposed publication for confidential information (other than study results) and for subject information subject to the HIPAA and other applicable privacy laws;
 - Review such proposed publication for the unauthorized use of the name, symbols and/or trademarks of Grifols;
 - By written notice to the investigator, identify with specificity the text or graphics in such proposed publication that Grifols contends contains confidential information, protected subject information, or the unauthorized use of Grifols' name, symbols and/or trademarks so that the proposed publication may be edited appropriately to remove such text or graphics before publication; and
 - By written request, Grifols may delay proposed publications up to sixty (60) days to allow Grifols to protect its interests in Grifols Inventions described in such publications.
4. Institution and/or investigator shall give Grifols the option of receiving an acknowledgment for its sponsorship of the study in all such publications or presentation.

REFERENCES

1. Human Plasma-derived Intravenous Fibrinogen Grifols Investigator's Brochure. Instituto Grifols, S.A. 2012.
2. Fibrinogen concentrate (Human), RiaSTAP™. [package insert]. Kankakee, IL. CSL Behring. 2009
3. CLOTTAGEN 1.5 g/100ml. [Résumé des Caractérisitques du Produit]. Les Ulis, France. LFB. 2002
4. Haemocomplettan® P. [Fachinformation]. Marburg, Germany. CSL Behring. 2007
5. EMEA (2009) Guideline on Core SmPC for Human Fibrinogen Products (EMEA/CHMP/BPWP/122007/2005).

## ABBREVIATIONS

$\alpha$	Alpha angle
ADR	Adverse drug reaction
AE	Adverse event
ALP	Alkaline phosphatase
ALT	Alanine aminotransferase
aPTT	Activated partial thromboplastin time
AST	Aspartate aminotransferase
ATC	Anatomical Therapeutic Chemical
ATIII	Antithrombin III
AUC	Area under the curve
AUC 0-14days	Area under the curve from zero to 14 days
AUC 0-∞	Area under the curve from zero to infinity
BUN	Blood urea nitrogen
CBC	Complete blood count
CFT	Clot formation time
CI	Confidence interval
Cl	Clearance
C max	Maximum plasma concentration
CSR	Clinical Study Report
CT	Clotting time
CV	Coefficient of variation
DBP	Diastolic blood pressure
dL	Deciliter
eCRF	Electronic Case Report Form
ELISA	Enzyme-linked immunosorbent assay
F1+2	Prothrombin fragments F1+2
FIB	Fibrinogen
Hct	Hematocrit
Hgb	Hemoglobin
HR	Heart rate
ICD-9-CM	International Classification of Diseases, Ninth Revision, Clinical Modification
IP	Investigational product
IVR	In vivo recovery
K el	Terminal first-order elimination rate constant
kg	Kilogram
LDH	Lactate dehydrogenase
LLOQ	Lower limit of quantification
MCF	Maximum clot firmness
MCH	Mean corpuscular hemoglobin
MCHC	Mean corpuscular hemoglobin concentration
MCV	Mean corpuscular volume

MedDRA	Medical Dictionary for Regulatory Activities
mg	Milligram
mL	Milliliter
MRT	Mean residence time
NAT	Nucleic acid amplification technology
Q1	25th percentile
Q3	75th percentile
PK	Pharmacokinetic
PP	Per-protocol
PT	Prothrombin time (according to the context)
PT	Preferred term (according to the context)
RBC	Red blood cells
ROTEM	Rotational thromboelastometry
RR	Respiration rate
SAE	Serious Adverse Event
SAP	Statistical Analysis Plan
SBP	Systolic blood pressure
SD	Standard deviation
SOC	System Organ Class
SOI	Start of Infusion
T	Temperature
$t_{1/2}$	Half-life
TAT	Thrombin-antithrombin III complex
TB	Total bilirubin
TEAE	Treatment emergent adverse event
$t_{max}$	Time to the observed maximum plasma concentration
TI	Time of infusion (i.e. length of infusion)
TT	Thrombin time
USA	United States of America
Vd	Volume of distribution
WBC	White blood cells
WHO-DD	World Health Organization Drug Dictionary

## 1 INTRODUCTION

This Statistical Analysis Plan (SAP) is based on Protocol IG0902 Version 2.3, dated 12Feb2016 and eCRF Version 5.0, dated 07Feb2017. The purpose of this SAP is to ensure that the statistical methodologies that will be used, and the data listings, summary tables and figures which will be produced, are appropriate and complete to support valid conclusions regarding the study objectives and the completion of the Clinical Study Report (CSR). Additional post-hoc or unplanned analyses, which are not defined in this SAP, may be performed to support the clinical development program. Such analyses will be documented in the CSR.

## 2 STUDY DESIGN AND OBJECTIVES

### 2.1 Study Design

This is a phase I-II, multi-center, prospective, open-label, single-arm clinical trial to evaluate the pharmacokinetics (PK), efficacy, and safety of human plasma-derived fibrinogen concentrate FIB Grifols in subjects with congenital fibrinogen deficiency manifested as afibrinogenemia.

In this clinical trial, the PK profile of the investigational product (IP) FIB Grifols will be established by measuring fibrinogen levels at different time points after a single-dose infusion of 70 mg/kg body weight. The hemostatic efficacy of FIB Grifols will be also established by means of rotational thromboelastometry (ROTEM) measures of maximum clot firmness (MCF) at baseline and 1-hour post-infusion.

Comparison of other thromboelastographic measures and standard coagulation tests before and after infusion at different time points will serve as secondary [REDACTED] endpoints indicative of hemostatic efficacy of the product. Safety of the product will be also studied by assessment of infusion tolerability, adverse events (AEs), and laboratory tests, including immunogenicity and virology testing.

This clinical trial is planned to be performed at sites in multiple countries including India, Italy (European Union), and the United States of America (USA). It is planned to include 11 adult subjects ( $\geq 18$  years) with congenital fibrinogen deficiency in order to provide at least 10 evaluable adult subjects. Only after the safety of FIB Grifols in adult subjects has been assessed and established by the sponsor, will the study start to enroll 11 pediatric subjects ( $< 18$  years) to achieve 10 evaluable pediatric subjects.

During the Screening Visit, the investigator will determine subject's eligibility for inclusion in the study. After giving informed consent and assent if applicable to participate in the clinical trial, subjects will be included in the *Subject's Screening Log* and they will be assessed using screening examinations. Eligible subjects will be treated with the investigational medicinal product under study and they will be included in the *Subject's Identification Log* by the investigator.

Throughout the clinical trial, several visits will be scheduled. Initial visits including Infusion Visit (Day 0) and Day 1 Visit will always be performed at the study center; however, the following visits may be performed by home health nurses at the subject's convenience: Day 2, Day 4, Day 6, Day 9, Day 14, Day 21 and Month 3 Visit (Month 3 Visit is applicable only for adult subjects).

It is required that Week 4 Visit is performed at the respective study center by the site investigative staff. Study assessments will comprise physical assessments, blood analysis, vital signs, and recording of AEs and concomitant medications.

The principal investigator at each site must be aware of and explicitly authorize the use of home health nurses service.

Home health nurses will not perform procedures or assessments that only a medically qualified physician (either the principal investigator or the designated sub-investigator) could do (i.e., physical assessment, AEs assessment or serious adverse events [SAEs] assessment). Home health nurses will only perform activities as indicated on the delegation of duties form. These will be limited to:

- Blood extraction and sample processing for shipment.
- Vital signs measurement (including heart rate [HR], respiration rate [RR], systolic and diastolic blood pressure [SBP and DBP], and temperature [T]).
- Subject interview and recording of potential AEs to be communicated to the principal investigator.
- Concomitant medications recording.

The overall study schema is shown in Figure 2-1.

[figure not shown]

Figure 2-1 Overall Study Schema and Study Visits

## 2.2 Study Objectives

### 2.2.1 Pharmacokinetic (PK) Objectives

To evaluate the PK profile of FIB Grifols following single-dose administration of 70 mg/kg body weight.

### 2.2.2 Efficacy Objectives

To evaluate hemostatic efficacy of FIB Grifols by means of thromboelastographic MCF values' comparison at baseline and one hour after IP administration. Other thromboelastographic measures as well as standard coagulation tests measured at different time points will also serve as secondary [REDACTED] efficacy endpoints.

### 2.2.3 Safety Objectives

To evaluate the safety of FIB Grifols, clinical safety, viral safety, and immunogenicity will be assessed in this clinical trial. Safety variables include AEs, vital signs, physical assessments, laboratory tests, viral markers, and antibodies against human fibrinogen.

## 3 STUDY VARIABLES

### 3.1 PK Variables

Plasma fibrinogen activity will be determined by the activity (Clauss) method and antigen method (enzyme-linked immunosorbent assay [ELISA]) in the central laboratory of the study. Fibrinogen activity levels will be determined immediately before infusion and at different time points after infusion.

The following PK parameters will be calculated for fibrinogen by a non-compartmental PK method determined from plasma levels before and at 30 minutes, 1 hour, 2 hours, 4 hours, 8 hours, 1 day (24 hours), 2 days (48 hours), 4 days (96 hours), 6 days (144 hours), 9 days (216 hours), and 14 days (336 hours) after the end of the infusion:

1. Area under the curve (AUC) including AUC from zero to 14 days ( $AUC_{0-14\text{days}}$ ) and AUC from zero to infinity ( $AUC_{0-\infty}$ )
2. Maximum plasma concentration ( $C_{\max}$ )
3. Time to the observed maximum plasma concentration ( $t_{\max}$ )
4. Half-life ( $t_{1/2}$ )
5. Mean residence time (MRT)
6. Volume of distribution (Vd)
7. Clearance (Cl)
8. In vivo recovery (IVR)

Incremental IVR will be calculated for fibrinogen levels from the peak level recorded within and including the first four hours after the end of infusion and reported as [mg/dL]/[mg/kg]. For the calculation of recovery, the declared potency of the investigational medicinal product actually administered to the subject will be considered in the calculation of dose administered, and the actual volume infused to the subject will also be used for calculating the dose administered to each subject.

The IVR will be determined for every subject using the following formula:

$$([FIB \ max \ (mg/dL)] - [FIB \ pre-infusion \ (mg/dL)]) / FIB \ administered \ (mg) / \text{Body weight (kg)}$$

where the *FIB max* is the peak FIB activity within the first four hours after the end of infusion and *FIB pre-infusion* is the baseline FIB activity level of the subject. *FIB administered* will be the actual administered dose calculated using the actual volume administered to the subject, the declared potency, and the true concentration of FIB in the batch used.

All PK parameters will be estimated using the fibrinogen concentration values obtained by both functional (Clauss) method and antigen (ELISA) method.

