4. TRIAL DESIGN

4.1 PHARMACOKINETIC ENDPOINTS

Plasma fibrinogen activity will be determined by the activity (Clauss) method and antigen method (enzyme-linked immunosorbent assay [ELISA]) in the central laboratory of the study. Fibrinogen activity levels will be determined immediately before infusion and at different time points after infusion.

The following PK parameters will be calculated for fibrinogen by a non-compartmental PK method determined from plasma levels before and at 30 minutes, 1 hour, 2 hours, 4 hours, 8 hours, 1 day (24 hours), 2 days (48 hours), 4 days (96 hours), 6 days (144 hours), 9 days (216 hours), and 14 days (336 hours) after the end of the infusion:

1. Area under the curve (AUC) including AUC from zero to 14 days ($AUC_{0-14\text{days}}$) and AUC from zero to infinity ($AUC_{0-\infty}$)
2. Maximum plasma concentration (C_{\max})
3. Time to the observed maximum plasma concentration (t_{\max})
4. Half-life ($t_{1/2}$)
5. Mean residence time (MRT)
6. Volume of distribution (Vd)
7. Clearance (Cl)

8. Incremental in vivo recovery (IVR)

Incremental IVR will be calculated for fibrinogen levels from the peak level recorded within and including the first 4 hours after the end of infusion and reported as $[\text{mg/dL}]/[\text{mg/kg}]$. For the calculation of recovery, the declared potency of the investigational medicinal product actually administered to the subject will be considered, and the actual volume infused to the subject will be used for calculating the dose administered to each subject.

The incremental IVR will be determined for every subject using the following formula:

$$([\text{FIB max (mg/dL)}] - [\text{FIB pre-infusion (mg/dL)}]) / \text{FIB administered (mg) / Body weight (kg)}$$

where the *FIB max* is the peak FIB activity within the first 4 hours after the end of infusion and *FIB pre-infusion* is the baseline FIB activity level of the subject. *FIB administered* will be the actual administered dose calculated using the actual volume administered to the subject, the declared potency, and the true concentration of FIB in the batch used.

All PK parameters will be estimated using the fibrinogen concentration values obtained by both functional (Clauss) method and antigen (ELISA) methods.

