^CBaseline (and subsequent) fibrinogen levels for PK calculations (Clauss and antigen methods [ELISA]) will be measured at the central laboratory of the study.

Table 4-5 Schedule of Procedures During Day 0 (Infusion Visit) in Pediatric Subjects

Procedures and assessments	Visits	Baseline (prior to infusion)	During infusion	After Infusion				
				30 minutes	1 hour	2 hours	4 hours	8 hours
Inclusion/Exclusion Criteria		X						
Height and Weight		X						
Physical Assessment		X						X
Medications ¹		X	X	X	X	X	X	X
Pregnancy Test ²		X ^A						
Serum Clinical Chemistry ³		X ^A						
Hematology ⁴		X						
Fibrinogen Levels (Clauss and Antigen)		X ^{A,B}		X ⁹	X	X ⁹	X ⁹	X
Rotational Thromboelastometry ⁵		X			X			
Standard Coagulation Tests ⁶		X			X			
Vital Signs ⁷		X	X		X			
Adverse Events		X	X	X	X	X	X	X
Thrombotic Events Risk Assessment		X			X		X	
Allergic/hypersensitivity Reactions Risk Assessment		X			X		X	
Retention Sample ⁸		X						
Footnotes continued on next page								

1. Concomitant medications.
2. Human chorionic gonadotropin (HCG)-based blood or urine assay for females of childbearing potential.
3. Creatinine, blood urea nitrogen (BUN), total bilirubin (TB), alkaline phosphatase (ALP), alanine aminotransferase (ALT), aspartate aminotransferase (AST), lactate dehydrogenase (LDH), glucose, sodium, potassium, chloride, and calcium.
4. Red blood cells (RBC) count, hemoglobin (Hgb), hematocrit (Hct), mean corpuscular hemoglobin (MCH), mean corpuscular hemoglobin concentration (MCHC), mean corpuscular volume (MCV), white blood cell (WBC) count and differential and platelet count.
5. Thromboelastographic parameters: clotting time (CT), clot formation time (CFT), maximum clot firmness (MCF), and alpha angle (α).
6. Thrombin time (TT), prothrombin time (PT) and activated partial thromboplastin time (aPTT).
7. Heart rate (HR), respiration rate (RR), systolic and diastolic blood pressure (SBP and DBP), and temperature (T).
8. A serum/plasma retention sample will be kept frozen at -70°C.
9. Not applicable for pediatric subjects weighing <30 kg.

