4.6.1.6 Fibrinogen Levels

Plasma samples will be obtained for measurement of fibrinogen levels by two methods:

1. Fibrinogen activity (Clauss method)
2. Fibrinogen antigen

Samples for fibrinogen determination will be taken at:

1. Screening Visit (up to 21 days prior to Infusion Visit): Sites that cannot perform fibrinogen levels determinations (by both Clauss and antigen method) locally will have a blood sample taken at Screening Visit and have it analyzed for this parameter by both methods at the central laboratory of the study for verification of the eligibility against the Inclusion/Exclusion criteria. In these cases, sample for the Inclusion/Exclusion criteria assessment will not be taken at Baseline Visit. Sample for PK will still be taken at Baseline Visit.

In order to allow sufficient time for samples shipment and analysis and reporting of results back to the site, the sample for determination of the eligibility should be drawn at least 14 days prior to the planned infusion.

2. Infusion Visit (Day 0):
 - i. For sites that have the capability of performing fibrinogen level determinations by both Clauss and antigen methods locally, a sample will be drawn within 24 hours of the scheduled infusion and analyzed at the local laboratory of the site in order to have the results available prior to the scheduled infusion in order to verify that the subject fulfills the inclusion criteria. In case fibrinogen levels determination for verification of the Inclusion/Exclusion criteria is performed at the screening visit, this sample will not be taken at Baseline Visit. Sample for PK as described below will still be taken at Baseline Visit.
 - ii. Immediately prior (within 60 minutes prior) to the scheduled infusion a sample will be taken and analyzed at the central laboratory for fibrinogen levels. The value to be used for PK calculations as baseline value will be the central laboratory one, unless there is any technical issue with the PK central laboratory measurement that recommends not using this value, in which case the value for the Inclusion/Exclusion criteria assessment could be used for this purpose.
 - iii. At 30 minutes (not applicable for pediatric subjects weighing <30 kg), 1 hour, 2 hours (not applicable for pediatric subjects weighing <30 kg), 4 hours (not applicable for pediatric subjects weighing <30 kg), and 8 hours after infusion end. These samples will be analyzed by central laboratory.

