8.2.4 LABORATORY PANELS

Laboratory tests will include:

1. Serum clinical chemistry: including creatinine, BUN, ALT, AST, ALP, LDH, TB, glucose, sodium, potassium, chloride and calcium.

2. Hematological parameters: CBC, including platelet count and differential leukocyte count.
3. Markers of activation of coagulation: different measures indicative of activation in the coagulation pathway (D-dimer, ATIII, TAT, F₁₊₂).

Blood specimens for laboratory tests will be collected at different time points throughout the study. Laboratory tests results will be collected in the corresponding CRF/eCRF entry. Abnormal (out of range) results will be flagged by the reporting laboratory. The investigator will be required to indicate the clinical relevance of out of range (abnormal) results. Laboratory results out of the normal range judged by the investigator as clinically relevant will be considered AEs.

In the case of markers of activation of coagulation, their relationship with plasma fibrinogen levels pre- and post-infusion will be studied.

In case of pediatric sampling, pediatric tubes would be provided to reduce the amount of blood drawn for lab works, including the complete elimination of virology, immunogenicity, and markers of activation of coagulation lab works. Pediatric subjects will not undergo Month 3 virology and immunogenicity follow-up visits, and their participation in the study will finish at the Week 4 Visit. Pediatric subjects weighing less than 30 kg will also have an even more reduced blood sampling schedule as detailed in [Table 4-4](#) and [Table 4-5](#):

- Day 0 - baseline (including the retention sample)
- Day 0 - 1 hour post-infusion
- Day 0 - 8 hours post-infusion
- Day 1 - 24 hours post-infusion
- Day 4 - 96 hours post-infusion
- Day 6 - 144 hours post-infusion and
- Day 9 - 216 hours post-infusion

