## **9 PK ANALYSIS**

PK analyses will be based on the PK population and will be performed on the adult and pediatric populations independently. PK analyses will be performed using the fibrinogen concentration values obtained by both Clauss method and antigen (ELISA) method.

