C max	the first observed peak plasma fibrinogen concentration following the end of drug infusion obtained directly from the experimental data without interpolation, expressed in concentration units (mg/dL).
t max	the observed time to reach peak plasma fibrinogen concentration obtained directly from the experimental data without interpolation, expressed in time units (hour).
t ½*	the terminal half-life, calculated as ln(2)/K el , expressed in time units (hour).
MRT*	mean residence time, calculated as AUMC 0-∞ /AUC 0-∞ -(TI/2), expressed in time units (hour), where AUMC 0-∞ is the area under the first moment of the concentration vs. time curve from time 0 extrapolated to infinite time, and TI is the length of infusion.*
Cl*	clearance, calculated as Dose/AUC 0-∞ , expressed in units dL/h/kg.
Vd*	volume of distribution, calculated as Cl × MRT, expressed in units dL/kg.

\*Parameters relying on the determination of the apparent terminal first-order elimination rate constant (Kel) will not be reported if R^2<0.8 or the extrapolated AUC to infinity is >20%.

Considering different potencies from different lots are administered, the actual dose amount (mg/kg) infused may deviate from the planned or target dose of 70 mg/kg. All appropriate PK parameters, such as AUC and Cmax, will be dose normalized to 70 mg/kg body weight after taking into account the actual potency. In addition, PK parameters corrected for the baseline fibrinogen level of the subject will be calculated for all the PK parameters above. The correction will be based on the fibrinogen concentration measured pre-infusion. The calculations will be the same as those described above for the un-corrected PK parameters, except the fibrinogen concentration measured pre-infusion will be deducted from the concentrations of each post-infusion sample before the calculations.

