### 9.3 Descriptive Statistics of PK Parameters

Descriptive statistics (summarized separately for adult and pediatric populations, including n, mean, SD, 90% CI for mean, %CV, median, minimum, and maximum will be calculated for all PK parameters. Geometric mean and 90% CI for geometric mean will also be calculated for all PK parameters (except  $t_{max}$ ). If data allow, PK parameters for the pediatric population will also be summarized by age group as appropriate (e.g. <2,  $\geq 2$  - <12,  $\geq 12$  - <18 years).

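### Peak recovery within 4 hours is not comparable across sampling schedules: children under 30 kg have one sample in the window, everyone else has four

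*SAP*

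**What the plan says.** **Definition.** SAP 3.1 and 9.2 compute incremental IVR "from the peak level recorded within and including the first four hours after the end of infusion", less the pre-infusion level, per mg/kg administered. Protocol 4.1 gives the same window and applies it to everyone: "The incremental IVR will be determined for every subject using the following formula". SAP 9.2 defines Cmax as "the first observed peak plasma fibrinogen concentration following the end of drug infusion", read from the data without interpolation.

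**Sampling.** Protocol 4.1 and SAP 3.1 list 11 post-infusion times with no weight exception: 0.5, 1, 2, 4, 8, 24, 48, 96, 144, 216 and 336 h. Protocol 4.6.1.6 then limits the Day 0 draws after the 30-minute one as follows: "1 hour, 2 hours (not applicable for pediatric subjects weighing <30 kg), 4 hours (not applicable for pediatric subjects weighing <30 kg"; the 30-minute draw carries the same restriction. Table 4-5, footnote 9, marks the same three cells "Not applicable for pediatric subjects weighing <30 kg". Protocol 8.2.4 confirms it ("Pediatric subjects weighing less than 30 kg will also have an even more reduced blood sampling schedule") and lists baseline, 1, 8, 24, 96, 144 and 216 h.

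**Summaries.** Under SAP 9 the PK analyses "will be performed on the adult and pediatric populations independently". SAP 9.3 gives one pediatric summary and one optional subdivision: "If data allow, PK parameters for the pediatric population will also be summarized by age group as appropriate". The SAP has no split by weight or schedule. Its pediatric column of nominal times in 4.1.1.1 shows all 11 times without qualification.

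**The concern.** A maximum depends on how many values it is taken over. The plan applies one rule, the peak within 4 h, to subjects with four chances to record a high value and to subjects with one. SAP 12 says the window was widened from 1 h to 4 h because Cmax seemed to occur between 1 and 2 h. For a child under 30 kg the widening adds no sample, so the stated reason for the definition does not reach this group.

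At stake is interpretation. A lower pediatric IVR, or a lower IVR in the youngest age band, could reflect fewer draws and not different kinetics. Age bands are the sharpest case: a band entirely under 30 kg set beside one entirely at or above it would show the whole subject-level gap. Cmax and tmax share the problem. IVR is a listed endpoint in a trial whose sample size rests on PK.

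**Working it through.** The plan states no figure for this effect, so there is none to reproduce.

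**1. Count the samples.**

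| Schedule | Up to 4 h | All post-infusion |
|---|---|---|
| Adults, children of 30 kg or more | 0.5, 1, 2, 4 h: 4 samples | 11 |
| Children under 30 kg | 1 h: 1 sample | 1, 8, 24, 96, 144, 216 h: 6 samples |

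Four is nominal: the 4 h draw has a 10-minute tolerance either side (Protocol 4.6.2), so a late draw can fall outside the window.

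**2. Direction.** The 1 h value is one of the four, so for any profile max(C0.5, C1, C2, C4) is at least C1. Baseline, dose and weight enter both versions identically. No assumption is needed.

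**3. Inputs for the size.** From the documents: half-life 3.0 to 5.3 days (Protocol 2.7). Assumed: assay CV 5% or 10%; within-subject error correlation 0, 0.5 or 0.8; 2, 5 or 8 of 10 children under 30 kg; baseline zero.

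**4. Subject-level gap** = E[max at 0.5, 1, 2, 4 h] / E[value at 1 h] − 1, from 400,000 simulated profiles per setting with multiplicative error. The declining shape is exponential from the end of infusion, with ranges spanning both half-lives and normal or lognormal error. The late-peak shape has true levels 0.95, 1 and 1.05 at 0.5, 1 and 2 h, then decline (half-life 4.0 days, normal error).

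| Shape | Errors | CV 5% | CV 10% |
|---|---|---|---|
| Declining | independent | 4.5–4.8% | 9.5–10.1% |
| Declining | correlation 0.5–0.8 | 1.9–3.3% | 4.0–6.9% |
| Late peak | independent | 7.8% | 12.3% |
| Late peak | correlation 0.5–0.8 | 5.7–6.6% | 7.3–9.5% |

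**5. How much is kinetics.** Without noise, the declining gap at a 4.0-day half-life is exp(0.5 × ln2/96) − 1 = 0.36%; the late-peak gap is 1.05/1 − 1 = 5.0%. At CV 5% the kinetic share is 0.36/4.61 = 8% (declining, independent) or 5.00/5.72 = 87% (late peak, correlation 0.8).

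**6. Against the true peak.** In the declining shape with normal error, the 1 h value is 0.3–0.5% below the highest true level at the sampling times, while the four-sample maximum is 1.4–9.5% above it. In the late-peak shape the 1 h value is 1 − 1/1.05 = 4.8% below.

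**7. Pooled pediatric mean.** With g = 1 + gap and m of 10 children under 30 kg, the shortfall against full sampling is 1 − [m + (10 − m)g]/(10g) = (m/10)(g − 1)/g.

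- Declining, independent (half-life 4.0 days): 0.9–3.5% at CV 5% and 1.8–7.1% at CV 10% for m = 2 to 8. Example: g = 1.046, m = 5 gives 0.5 × 0.046/1.046 = 2.2%.
- Declining, correlated: 0.4–2.5% and 0.8–5.0%.
- Late peak, independent: at CV 5%, 0.2 × 0.078/1.078 = 1.4% to 0.8 × 0.078/1.078 = 5.8%; at CV 10%, 0.2 × 0.123/1.123 = 2.2% to 0.8 × 0.123/1.123 = 8.8%.
- m = 0: zero.

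**8. Scale.** The planned 90% CI at n = 10 has half-width 1.833 × CV/√10, which is 5.8%, 11.6% or 17.4% of the mean for an assumed between-subject CV of 10%, 20% or 30%.

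**9. Cmax and tmax, declining shape.** The full-to-reduced Cmax gap is 3.6–4.0% (CV 5%) and 6.0–7.1% (CV 10%) with independent errors, and 1.8–2.9% and 3.3–5.4% correlated. Some 62–68% of fully sampled subjects peak at a time absent from the reduced schedule.

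**10. Are low-weight children plausible?** Dose volume is 70 × 0.05 = 3.5 mL/kg (Protocol 4.5.4.1), the maximum rate is 5 mL/min, and SAP 4.1.1.1 gives a mean pediatric infusion of 0.5 h. If that mean is accurate, mean weight is at most 30 × 5/3.5 = 43 kg. The SAP also anticipates bands under 2 and from 2 to under 12 years. This makes children under 30 kg likely but proves none.

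**The case against.** A reader might infer that pediatric IVR is simply biased low. The documents do not support that as a general statement. It needs a reference value, and steps 5 and 6 show that when levels decline from the end of infusion, nearly all the gap is upward bias in the fully sampled subjects. With 5 of 10 children under 30 kg, CV 5% and independent errors, the pooled pediatric mean is then about 2% above the truth. Low against the true peak needs a peak away from 1 h. SAP 12 suggests one between 1 and 2 h, but only from a preliminary look at the data. A reader might also infer that adults and children are pooled; SAP 9 and 9.3 keep them apart.

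Other points stand in part:

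- No test, acceptance limit or formal adult–child comparison of IVR is planned, and the age split is conditional. This limits the importance.
- The reduced schedule is deliberate, limits blood volume and is openly stated. The objection here is to the analysis, not the sampling.
- SAP 9.1 already lists concentrations, doses and potency and summarises the 1 h level. But no dose-adjusted 1 h recovery is planned, so readers would have to build the comparison themselves.
- The SAP cites Protocol 2.3. Whether that version contained the 30 kg rule cannot be checked, so the SAP's silence may reflect timing.
- SAP 4.1.1.3 allows interpolation of missing values if necessary, but does not say that unscheduled samples count as missing, and one early sample cannot recover a peak.

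**Conclusion.** The point holds as non-comparability with a known direction. For the same kinetics, the one-sample IVR is equal to or below the four-sample IVR. The pediatric IVR, Cmax and tmax summaries, the optional age bands and any adult–child reading therefore mix kinetics with sampling.

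The direction is certain; the size is not. It rests on an assay CV, an error correlation and a number of children under 30 kg that the documents do not give. Under the assumptions above, the subject-level gap is 1.9–10.1% for declining levels and 5.7–12.3% for a late peak. The pooled shift usually lies within the planned 90% CI, and it vanishes if no child is under 30 kg. PK is descriptive, so no hypothesis test changes. The SAP should be amended, but the trial's conclusions are not threatened.

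**What to change.** Keep the protocol-defined peak IVR as the main parameter.

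- **SAP 9.2, add:** As a supportive analysis, IVR(1h) is calculated from the 1-hour post-infusion sample for every subject, with the same baseline, dose and weight terms, for Clauss and antigen, and is reported beside peak IVR for adults and for children.
- **SAP 9.3, add:** Pediatric peak IVR, Cmax and tmax are also presented by sampling schedule (<30 kg versus ≥30 kg; individual values if a stratum is small), with a footnote on the reduced schedule (1 versus 4 samples up to 4 h; 6 versus 11 overall). Adult–child or age-band differences in peak IVR are to be read against IVR(1h).

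With one sample against one sample, IVR(1h) removes the difference caused by the schedule. The cost is SAP wording, one derived variable and one split table; no samples are added. With about 10 children the strata will be small, and IVR(1h) can miss a later peak, so it is supportive only.
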